#### 8.1.6 Serious Adverse Device Effect

A serious adverse device effect (SADE) is an adverse event that is both serious and device related.

#### 8.1.7 Unanticipated Adverse Device Effect

An unanticipated adverse device effect (UADE) means any serious adverse effect on health or safety or any life-threatening problem or death caused by, or associated with, a device, if that effect, problem or death was not previously identified in nature, severity, or degree of incidence in the investigational plan

Protocol no: NSM-004; Version 21.0 Page 103 of 141 04 Apr 2025
Confidential Neuspera

or application (including a supplementary plan or application), or any other unanticipated serious problem associated with a device that relates to the rights, safety or welfare of subjects.

An event will not be considered a UADE if it is a known consequence of the underlying disease or condition under investigation, surgery, or other events that commonly occur in the study population independent of the investigational device.

The final determination of whether an AE meets the definition of a UADE will be made by the independent Clinical Events Committee for this study.

#### 8.1.8 Unanticipated Serious Adverse Device Effect

An unanticipated serious adverse device effect (USADE) is any serious adverse device effect which by nature, incidence, severity or outcome has not been identified in the current risk assessment.

An event will not be considered a USADE if it is a known consequence of the underlying disease or condition under investigation, surgery, or other events that commonly occur in the study population independent of the investigational device.

The final determination of whether an AE meets the definition of a USADE will be made by the independent Clinical Events Committee for this study.

#### 8.1.9 Anticipated Serious Adverse Device Effect

An anticipated serious adverse device effect (ASADE) is an effect which by its nature, incidence, severity or outcome has been identified in the risk analysis report.

#### 8.2 Adverse Events Causality and Severity Rating

#### 8.2.1 Causality

Safety reporting in clinical investigations of medical devices will be performed in line with the requirements of the Regulation (EU) 2017/745: Medical Device Regulation (MDR) Article 80(2), including the guidance document MDCG 2020-10/1. The relationship between the use of the investigational device (including the medical-surgical procedure) and the occurrence of each serious adverse event will be assessed and categorized using terms below. This guidance document only applies to serious adverse events; however, for ease of investigator reporting, Neuspera will use the same categorization terms for both serious adverse events and non-serious adverse events.

The investigator must specify whether an adverse event has a causal relationship to one of the following:

- **Study device:** Involves function of the device, or the presence of the device in the body, events directly related to the device.
- **Implant procedure:** Results from the implant procedure, including events directly related to the general procedural sequelae.
- **Subject's condition:** Results from the worsening of a pre-existing condition or cannot be attributed to the device procedure.
- Unknown: Cannot be assigned to any of the above three conditions.

Protocol no: NSM-004; Version 21.0 Page 104 of 141 04 Apr 2025
Confidential Neuspera

The causal relationship of an adverse event to the investigational device or implant procedure will be rated as follows:

- Not related: Relationship to the device, comparator or procedure can be excluded when:
  - the event has no temporal relationship with the use of the investigational device or the procedures related to application of the investigational device;
  - the serious adverse event does not follow a known response pattern to the medical device (if the response pattern is previously known) and is biologically implausible;
  - the discontinuation of medical device application or the reduction of the level of activation/exposure when clinically feasible and reintroduction of its use (or increase of the level of activation/exposure), do not impact on the serious adverse event;
  - the event involves a body-site or an organ that cannot be affected by the device or procedure;
  - the serious adverse event can be attributed to another cause (e.g. an underlying or concurrent illness/ clinical condition, an effect of another device, drug, treatment or other risk factors);
  - the event does not depend on a false result given by the investigational device used for diagnosis, when applicable;

In order to establish the non-relatedness, not all the criteria listed above might be met at the same time, depending on the type of device/procedures and the serious adverse event.

- **Possible:** The relationship with the use of the investigational device or comparator, or the relationship with procedures, is weak but cannot be ruled out completely. Alternative causes are also possible (e.g. an underlying or concurrent illness/ clinical condition or/and an effect of another device, drug or treatment). Cases where relatedness cannot be assessed or no information has been obtained should also be classified as possible.
- **Probable:** The relationship with the use of the investigational device or comparator, or the relationship with procedures, seems relevant and/or the event cannot reasonably be explained by another cause.
- **Causal relationship:** the serious adverse event is associated with the investigational device, comparator, or with procedures beyond reasonable doubt when:
  - the event is a known side effect of the product category the device belongs to or of similar devices and procedures;
  - the event has a temporal relationship with investigational device use/application or procedures;
  - the event involves a body-site or organ that
    - the investigational device or procedures are applied to;

Protocol no: NSM-004; Version 21.0 Page 105 of 141 04 Apr 2025
Confidential Neuspera

<sup>4 If an investigational device gives an incorrect diagnosis, the patient might, for example, receive an unnecessary treatment and incur all the risks that accompany that treatment, or might be incorrectly diagnosed with a serious disease. In other cases, the patient might not receive an effective treatment (thereby missing out on the benefits that treatment would confer), or might not be diagnosed with the correct disease or condition.

- the investigational device or procedures have an effect on;
- the serious event follows a known response pattern to the medical device (if the response pattern is previously known);
- the discontinuation of medical device application (or reduction of the level of activation/exposure) and reintroduction of its use (or increase of the level of activation/exposure), impact on the serious adverse event (when clinically feasible);
- other possible causes (e.g. an underlying or concurrent illness/clinical condition or/and an effect of another device, drug or treatment) have been adequately ruled out;
- harm to the subject is due to error in use;
- the event depends on a false result given by the investigational device used for diagnosis, when applicable;

In order to establish the relatedness, not all the criteria listed above might be met at the same time, depending on the type of device/procedures and the serious adverse event.

The adjudication decision of the CEC will be used for the final classification of events, including relatedness to the study procedures and/or the investigational device, for the determination of safety endpoints and for all regulatory reports, product labeling, and publications or presentations.

Protocol no: NSM-004; Version 21.0 Page 106 of 141 04 Apr 2025 Confidential Neuspera

<sup>5 If an investigational device gives an incorrect diagnosis, the patient might, for example, receive an unnecessary treatment and incur all the risks that accompany that treatment, or might be incorrectly diagnosed with a serious disease. In other cases, the patient might not receive an effective treatment (thereby missing out on the benefits that treatment would confer), or might not be diagnosed with the correct disease or condition.

### 8.2.2 Severity

All adverse events will have a severity classification according to the Clavien-Dindo classification system. 12,13

Grades	Definitions
Grade I	Any deviation from the normal postoperative course without the need for pharmacological treatment or surgical, endoscopic, and radiological interventions. Acceptable therapeutic regimens are: drugs such as antiemetics, antipyretics, analgesics, diuretics, and electrolytes, and physiotherapy. This grade also includes wound infections opened at the bedside.
Grade II	Requiring pharmacological treatment with drugs other than those allowed for grade I complications. Blood transfusions and total parenteral nutrition are also included.
Grade III	Requiring surgical, endoscopic, or radiological intervention
Grade III-a	Intervention not under general anesthesia
Grade III-b	Intervention under general anesthesia
Grade IV	Life-threatening complication (including CNS complications: brain hemorrhage, ischemic stroke, subarachnoid bleeding, but excluding transient ischemic attacks) requiring IC (intermediate care)/ICU (intensive care unit) management
Grade IV-a	Single organ dysfunction (including dialysis)
Grade IV-b	Multi-organ dysfunction
Grade V	Death of a patient
Suffix "d"	If the patient suffers from a complication at the time of discharge the suffix "d" (for disability) is added to the respective grade of complication. This label indicates the need for a follow-up to evaluate the complication fully.

# 8.3 Foreseeable Adverse Events and Anticipated Adverse Device Effects

See Section 4.4 for risks associated with the Neuspera's Implantable SNS System.

# 8.4 Reporting Requirements

# 8.4.1 Adverse Event Recording

Investigators are responsible for providing a description of all AEs, including the date of the event, treatment, and the clinical outcomes for the subject. Investigators will evaluate each event for seriousness, severity and relatedness to the procedure, device, or stimulation therapy. Investigators must supply the Sponsor with additional information related to safety reporting of a particular event.

Pre-existing conditions must be documented as medical history so that related AEs can be correctly recorded. An event that is a continuation of an unresolved AE must be recorded as ongoing, not as a new AE. Worsening of a pre-existing condition must be recorded. Complications and hospitalizations must also be recorded.

Sponsor shall fully record any adverse event of a type identified in the clinical investigation plan as being critical to the evaluation of the results of the clinical investigation.

Protocol no: NSM-004; Version 21.0 Page 107 of 141 04 Apr 2025 Confidential Neuspera

#### 8.4.2 Adverse Event Reporting

Investigators are required to report all AEs during the course of the study (except as outlined below).

Investigators shall report AEs to the Sponsor, and to their reviewing IRB/ECs per the IRB/EC reporting requirements.

Investigators are required to report UADEs to the Sponsor and their reviewing IRB as soon as possible but in no event later than 10 working days after the Investigator first learns of the effect, per 21 CFR 812.150. Per MDCG 2020-10/1, UADE shall immediately be reported by the investigators, but no later than 3 calendar days after investigational site study personnel's awareness of the event.

AE reporting exceptions:

AEs that would be reasonably expected to be associated with any surgical procedure (e.g.
anesthesia associated symptoms, surgical site pain, post- procedure pain) will not be required to
be reported as AEs unless, in the opinion of the Investigator, the nature and/or severity is
outside of what is typical for SNS procedures and recovery.

#### 8.4.4 Reporting Device Deficiencies

Investigators are responsible for providing a description of all device deficiencies, including any impact on the subject. Notification of device deficiencies should be made to the Sponsor or representative as soon as possible for appropriate investigation. Device deficiencies are reported on the appropriate case report form.

The investigator shall report initially (and any new findings) and the sponsor shall fully record and report without delay to all EU Member states in which the study is occurring any device deficiency that might have led to a serious adverse event if appropriate action had not been taken, intervention had not occurred, or circumstances had been less fortunate. Sponsor shall report this without delay per applicable guidelines and local regulations.

The period for reporting shall take account of the severity of the event. Where necessary to ensure timely reporting, the sponsor may submit an initial report that is incomplete followed up by a complete report.

Protocol no: NSM-004; Version 21.0 Page 108 of 141 04 Apr 2025
Confidential Neuspera

### 8.4.4.1 Events or Malfunctions (Lead Migration/Dislodgement, Fractures, Revisions)

Investigators shall report to Neuspera as soon as possible but no event later than 30 working days after the investigator first learns of the effect of all device events or malfunctions, that is, lead migration/dislodgement and fractures, whether clinically significant or not. In addition, a further breakdown of how device events or malfunctions are dealt with will be provided (e.g. no action needed, reprogramming, permanent loss of therapy and/or surgical revision/explantation). These events will be recorded by subject and event, since multiple events may occur in a single subject.

All events (lead migration/dislodgement and fractures), whether determined to be clinically significant or non-clinically significant, will be identified and reported to the DSMB and the FDA as soon as possible but in no event later than 10 working days after Neuspera first receives notice of the event from the clinical investigator.

Clinically significant events are those events that can only be corrected by surgical revision or result in permanent loss of therapy. If the therapy is still providing benefit after reprogramming, Neuspera considers the event not to be clinically significant. Any investigator who corrects a clinically significant event of lead migration/dislodgement, fracture, and loss of therapy with a revision surgery will be asked to notify Neuspera as soon as possible but in no event later than 30 working days after the investigator completes the revision surgery. Neuspera anticipates that Field Clinical Engineers will support all revision surgeries, and Neuspera will then report any clinically significant events of lead migration/dislodgement, fracture, and loss of therapy corrected by revision surgery to the FDA and DSMB as soon as possible but in no event later than 10 working days.

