#### 6.4 Study Stopping Rules for Phase II

Phase II will use stopping rules designed to suspend enrollment and trigger a series of events if at any time there is sufficient statistical evidence to conclude that any of the Phase II probabilities of device fracture, device dislodgement/migration, or surgical revision exceed comparator probabilities from an approved device. The comparator probabilities are shown in Table 5.

TABLE 5: COMPARATOR EVENT PROBABILITIES GUIDING THE PHASE II STOPPING RULE. VALUES SHOWN ARE POINT ESTIMATES (UPPER LIMITS OF 95% CONFIDENCE INTERVALS).

Event Type	Proportion of Subjects with Event
Fractures	0.014 (0.022)1
Dislodgements/Migrations	0.026 (0.036) 

<sup>1 Based on Medtronic's 2020 Product Performance Report showing 19 subjects experienced lead fractures out of 1,314 subjects followed (page 167).

Page 70 of 141 04 Apr 2025 Confidential Neuspera

<sup>2 Based on Medtronic's 2020 Performance Report showing 34 subject experienced lead dislodgements/migrations out of 1,314 subjects followed (page 167).

Surgical Revisions	0.118 (0.239) 

Phase II will use the following stopping rule. At each occurrence of device fracture, dislodgement/migration, or surgical revision, form an exact one-sided binomial confidence interval for the event probability. Determine whether any of the following conditions is met:

- The lower limit of the interval for device fractures exceeds 0.014.
- The lower limit of the interval for device dislodgements/migrations exceeds 0.026.
- The lower limit of the interval for surgical revisions exceeds 0.118.

The numerator for each event is the number of subjects who have experienced the event up to that time. The denominator will be the number of subjects implanted up to that time. For device fractures and migrations/dislodgements, the confidence level of the interval will be 95%. For surgical revisions, the confidence level will be 80% if 50 or fewer subjects have been implanted; if more than 50 subjects have been implanted, the confidence level will be 95%. If any of the above conditions is met, the following actions will be taken:

- Both enrollment and implants will be suspended, and FDA will be notified within 7 days
- Neuspera will conduct a root cause analysis to determine the cause of the safety events that triggered the stopping rule
- Neuspera will prepare a safety report for submission to the DSMB

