#### 11.7 Investigator Disqualification Criteria

Neuspera reserves the right to terminate an investigator/investigational site for any of the following reasons:

- Failure to secure subject informed consent including protection of personal data prior to enrollment
- Failure to report safety events within 10 working days of discovery after learning of the event
- Failure to report serious adverse device effects within 10 working days of discovery
- Repeated investigational plan deviations
- Repeated failure to appropriately complete case report forms
- Failure to enroll an adequate number of subjects
- Loss of or unaccounted for investigational product inventory

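### The 30-working-day ceiling on site reports of fractures and dislodgements does not fit the stopping rule these events feed, or the 10-working-day limit in Section 11.7

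*Protocol*

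**What the plan says.** **Site to sponsor.** Protocol Section 8.4.4.1 covers every lead migration/dislodgement and fracture, clinically significant or not. The duty is to report as soon as possible, with a ceiling of "no event later than 30 working days after the investigator first learns of the effect". Where a clinically significant event is corrected by revision surgery, the ceiling is "in no event later than 30 working days after the investigator completes the revision surgery".

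**Sponsor to DSMB and FDA.** The same section gives the sponsor a further step, "in no event later than 10 working days after Neuspera first receives notice of the event from the clinical investigator".

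**Stopping rule.** Protocol Section 6.4, repeated in SAP Section 8, works event by event: "At each occurrence of device fracture, dislodgement/migration, or surgical revision, form an exact one-sided binomial confidence interval for the event probability". The numerator is subjects with the event to date. On the other count, "The denominator will be the number of subjects implanted up to that time". If a lower limit passes its comparator, enrollment and implants are suspended and FDA is told within 7 days. Section 6.4 refers to the events that set off the rule as safety events.

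**Site termination.** Protocol Section 11.7 lists, among the reasons for which the sponsor may terminate a site, "Failure to report safety events within 10 working days of discovery after learning of the event". Serious adverse device effects have their own line in that list, so the safety-events line is wider than those.

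**The concern.** The stopping rule can act only on events the sponsor knows about. Its first input may lawfully arrive 30 working days after the site became aware, three times the sponsor's own 10-working-day step and much longer than the 7 days allowed for telling FDA of a trigger. While implanting was under way, more subjects could receive the device in that interval. Because the denominator grows with each implant, late notice could also make a crossed limit look uncrossed, unless the counts are taken back to the event date.

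Sites face a separate problem. One that reports a dislodgement on working day 25 complies with Section 8.4.4.1, yet on a natural reading of Section 11.7 has given the sponsor a reason to terminate it. The available text does not say which limit governs.

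**Working it through.** **1. The plan's own figures.** Section 6.4 derives its comparators from 19/1314, 34/1314 and 6/51. Exact two-sided 95% limits give:

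- fractures 0.0145, upper limit 0.0225 (plan: 0.014, 0.022)
- dislodgements 0.0259, upper limit 0.0360 (plan: 0.026, 0.036)
- revisions 0.1176, upper limit 0.2387 (plan: 0.118, 0.239)

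The early revision trigger also holds: the 80% one-sided lower limit is 0.157 for 4/15, above 0.118, and 0.104 for 3/15, below it. The rule's arithmetic is not in dispute.

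**2. Implants during the reporting interval.** Inputs: 120 attempted implants and about 114 successful (Synopsis, Sample size); about 12 months' enrollment (Section 5.3). Assumptions: even accrual, 260 working days a year, and a site that uses the whole allowance. Implants in the interval = N / working days in the accrual period × working days of delay.

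| Accrual | 10 working days | 30 working days |
|---|---|---|
| 120 in 12 months (120/260 = 0.462 a day) | 4.6 | 13.8 |
| 114 in 12 months (114/260 = 0.438 a day) | 4.4 | 13.2 |
| 120 in 18 months (assumed; 120/390 = 0.308 a day) | 3.1 | 9.2 |
| 114 in 18 months (assumed; 114/390 = 0.292 a day) | 2.9 | 8.8 |

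In calendar time, 30 working days is 30/5 × 7 = 42 days and 10 working days is 14.

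**3. Can late notice hide a trigger?** The exact one-sided 95% lower limit is the 0.05 quantile of Beta(x, n − x + 1). Triggers are small counts:

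- fractures: 2 for 16–25 implanted, 3 for 26–59, 4 for 60–98
- dislodgements: 3 for 16–32 implanted, 4 for 33–53, 5 for 54–76, 6 for 77–101

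Comparing the denominator at the event with the denominator 14 implants later:

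- fractures: 2/25 gives 0.0144, above 0.014; 2/39 gives 0.0092, below it
- dislodgements: 3/32 gives 0.0260, just above 0.026; 3/46 gives 0.0180, below it

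So if the limit is calculated with the denominator at receipt, 14 extra implants erase every two-fracture trigger between 16 and 25 implanted (16 + 14 = 30, where 2/30 gives 0.0120). A 10-working-day lag of about 5 implants erases fewer: 2/20 becomes 2/25 and still triggers, but 2/25 becomes 2/30 and does not. A shorter deadline alone therefore does not close the gap; the counts must be fixed at the event date.

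**4. Position now.** Section 3.1.2.2.2 reports 130 attempted implants, two subjects with fracture, four with clinically significant dislodgement, one further dislodgement that was not clinically significant, and four with revision. Using 130 as the denominator, and five subjects with dislodgement at most, the 95% lower limits are 0.0027 (fractures), 0.0153 (dislodgements) and 0.0106 (revisions). All are below the thresholds. With 124 implanted (130 × 0.95, rounded up), fractures give 0.0029 and dislodgements 0.0160, also below.

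**The case against.** Much of the other side stands.

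- Thirty working days is a ceiling on a duty to report as soon as possible, not the expected interval.
- Section 11.7 reserves a right to terminate; nothing is automatic. It does not define safety events, so the conflict rests on the use of that term in Section 6.4. One can argue that Section 8.4.4.1, as the specific provision, governs. Section 8.4.3 is not in the text available for this review, so reconciling wording there cannot be excluded.
- Section 8.4.4.1 anticipates sponsor field engineers at all revision surgeries, and the sponsor must be contacted when a device is explanted or replaced (Sections 7.5.8.9 and 7.5.8.10). The sponsor would normally learn of revisions at about the time of surgery. This does not cover events managed without surgery.
- Serious adverse device effects already carry a 10-working-day limit, or less (Section 8.4.5).
- With 130 attempts reported against a target of 120, there is little or no implanting left to suspend. The figures in step 2 describe the design, not future exposure.

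A reader might infer that the stopping rule cannot work, or that a trigger was missed. The documents do not support either. The rule's counts are defined up to the time of the event, so a late report can still be evaluated at its own denominator; the trigger is then delayed, not lost. The reported totals lie below the limits, and no event dates are given from which a missed trigger could be shown.

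A reader might also add the sponsor's 10 working days and speak of 17 to 18 implants before action (40 × 0.438 = 17.5; 40 × 0.462 = 18.5). That is the delay until the DSMB and FDA hear. Section 6.4 lists suspension before the report to the DSMB, so it is not shown to be the delay until suspension.

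**Conclusion.** The point holds in limited form. The site limits in Sections 8.4.4.1 and 11.7 conflict on a natural reading. The 30-working-day ceiling also weakened the stopping rule as designed, by about 13 to 14 implants against 4 to 5 over 12 months, or about 9 against 3 over an assumed 18. These figures assume even accrual and full use of the allowance. The loss of a trigger, as opposed to its delay, further requires that the denominator be taken at receipt, a reading Section 6.4 should expressly rule out.

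For the current version the consequence is smaller. It concerns mainly how quickly the sponsor, DSMB and FDA learn of fractures and dislodgements during follow-up, which Section 5.3 puts at up to 36 months or longer for some subjects. It matters most for events managed without surgery that are not serious adverse device effects.

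**What to change.** In Protocol Section 8.4.4.1, replace the two 30-working-day ceilings with one site reporting limit for fractures, dislodgements/migrations and revisions, no longer than the 10 working days in Section 11.7. State in Section 11.7 that safety events include these events. Cross-refer both to Section 6.4, and add there and in SAP Section 8 that, on receipt of a report, the stopping limits are calculated with the numerator and denominator as of the event date. An instruction merely to recalculate on receipt would not do, because it could be read as using the later, larger denominator.

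The cost is protocol and SAP wording, a notice to sites, and slightly faster paperwork. No treatment, visit, endpoint or efficacy analysis changes.
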